### **Objective(s) of the Study:**

The aim of this study was to determine the immunomodulating effect of *N. sativa* on T lymphocyte cell activity, various inflammatory cytokines, and SLEDAI Score in paediatric SLE patients.

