### **Study design :**

This is a clinical trial study, pre and post test control group design, that has received permission from the ethics committee of Health Research Ethics Commission General Hospital [name] Malang with number (400/089/K3/302/2021). The research design is single blind and uses a placebo group as the control.

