### **Methods:**

A total of 32 SLE paediatric patients were randomly divided into two groups, the *N. sativa* oil treatment group and the placebo group. Each patient consumed 1 gram of *N. sativa* oil capsule or 1 gram of starch capsule daily for 8 weeks. *N. sativa* oil capsules were purchased from CV Rizki Abadi, Tuban, East Java, Indonesia, (POM TR.183314171). Standard therapy in all patients was Prednisone, Hydroxychloroquine, and Mycophenolate acid. Every week, the research team monitored the patients by phone to determine the progress of the patients' condition and any possible side effects.

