### **Research Procedures**

#### **1. Blood Collection**

Blood samples were taken twice, at the beginning of the study and at the end of the treatment at the RSSA Clinical Pathology Laboratory by laboratory staff. The volume of blood taken in each research sample was 8 ml. Furthermore, blood samples were made serum through a centrifugation process at 3000 rpm for 5 minutes, and stored at 4°C for measurement of the patient's immunological profile.

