#### **2. Measurement of T lymphocyte cell profile**

From the peripheral blood samples obtained earlier, PBMC isolation was carried out. PBMCs were isolated using Ficoll gradient density centrifugation. The PBMC suspension was incubated overnight at 37°C in RPMI 1640 media with 100 U/mL penicillin and streptomycin, 2 mM glutamine, and 10% FBS. The PBMCs were collected, washed, and stained with fluorescein isothiocyanate-conjugated anti-human CD4. After surface labeling, cells were stained with phycoerythrin (PE)-conjugated anti-human IFN-γ to identify Th1. Th2 detection was carried out using PE-conjugated anti-human IL-4. Treg detection was performed using CD25+Foxp3-PE antibodies. Th17 identification was carried out using CD4+IL-17A-PE antibodies. All antibodies were using brands from BD Bioscience (San Jose, US).

Afterwards, the analysis was carried out using a BD FACS Calibur flow cytometer (Becton Dickinson, USA). The cell population percentages were organized and analyzed using the CELL Quest pro software application.

3. Measurement of cytokine levels

Serum levels of IFN- $\gamma$ , TNF- $\alpha$ , IL-2, IL-4, IL-6, IL-17, and IL-10 were measured at both baseline and endpoint of the trial. They were measured using commercially available cytokine CBA (Cytometric Bead Array) flow cytometry kits, which can measure multiple analytes at the same time. All antibodies were using brands from Becton Dickinson (US) and the software to analyse it was CELL Quest Pro Software from Becton Dickinson (New Jersey, USA).

4. Scoring SLEDAI

SLE disease activity was measured using SLEDAI 2K. The data required are clinical manifestations, including arthritis, fever, elevated dsDNA, and other conditions such as photosensitivity and arthralgia. Each clinical manifestation was given a score, and the scores were then summed to obtain the total SLEDAI 2K score.

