**Statistical analysis**

Data for each patient were collected in the form of a data collection sheet. Numerical data were analysed by Independent T Test if the data were normally distributed or by Mann-Whitney test if the data were not normally distributed. For pre and post treatment, each group (N. sativa treatment and placebo), if normally distributed using Paired T Test, but if not normally distributed using Wilcoxon test. Statistical tests were considered meaningful if the p value was  $\leq 0.05$ . All calculations were performed with the help of SPSS for Windows 25.0 software.

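### The between-arm test has no stated variable or deciding role and no baseline adjustment; a baseline-adjusted comparison at week 8 should decide, with within-arm tests descriptive only

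*Combined protocol and SAP*

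**What the plan says.** The Statistical analysis section of the combined protocol and SAP is one short paragraph. Its between-arm sentence reads "Numerical data were analysed by Independent T Test if the data were normally distributed or by Mann-Whitney test", with Mann-Whitney for non-normal data. It gives no variable (baseline, end of treatment or change) and does not call this test the deciding one.

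The next sentence is the only one that mentions before-and-after values, and it concerns each arm separately: "For pre and post treatment, each group (N. sativa treatment and placebo), if normally distributed using Paired T Test", otherwise Wilcoxon. One criterion then covers everything: "Statistical tests were considered meaningful if the p value was" at most 0.05. No baseline-adjusted analysis is named.

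Elsewhere the plan describes a "pre and post test control group design" with placebo as control (Study design). Methods states "A total of 32 SLE paediatric patients were randomly divided into two groups", with 8 weeks of treatment. The objective is the effect of *N. sativa* on "T lymphocyte cell activity, various inflammatory cytokines, and SLEDAI Score in paediatric SLE patients".

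Baseline values exist for the laboratory outcomes. Under Blood Collection, "Blood samples were taken twice, at the beginning of the study and at the end of the treatment"; under Measurement of cytokine levels, the seven cytokines "were measured at both baseline and endpoint of the trial". The paragraph on SLEDAI scoring gives no assessment times. That SLEDAI is scored twice can be inferred only from the pre/post design.

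**The concern.** The objective is a treatment effect, and in a randomised placebo-controlled trial only a comparison of the arms estimates it. On week-8 or change values the named independent test would be a valid comparison. On baseline values it would say nothing about treatment. The text does not settle which is meant.

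Three things are at stake:

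- **Precision.** With 32 patients, an unadjusted two-sample test may discard information that the baseline samples already provide.
- **A choice after results.** If the variable is open between week-8 and change, the more favourable one can be picked for each outcome.
- **Misreading of the within-arm tests.** All patients receive standard background therapy, so both arms may change over 8 weeks. A paired test within one arm cannot separate a shared change from an effect of *N. sativa*. The plan gives these tests the same threshold as the between-arm test and no lesser role.

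**Working it through.** The plan gives no power, SD, expected effect or pre-post correlation, so there is no figure of its own to reproduce.

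**Inputs.** From the documents: 32 patients, two arms, p ≤ 0.05. Assumed: 16 per arm (the split is not stated), two-sided tests, normal data, equal SDs, and a pre-post correlation ρ from 0 to 0.7. Week 8 means end of treatment.

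**1. Precision.** Error variance relative to week-8 values:

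- week-8 t-test: 1
- t-test on change: 2(1 − ρ)
- ANCOVA: (1 − ρ²) × [1 + 1/(2n − 4)]. The bracket allows for chance baseline imbalance; with n = 16 it is 1 + 1/28 = 1.036.

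At ρ = 0.5, change gives 2 × 0.5 = 1.00 and ANCOVA gives 0.75 × 1.036 = 0.777.

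With s the square root of the relative variance, the detectable difference δ (in SD of week-8 values) solves P(T > t₀.₉₇₅) = 0.80. T is noncentral t with noncentrality δ / (s√(2/16)), on 30 df for the t-tests and 29 for ANCOVA.

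| ρ | Week-8 t | Change t | ANCOVA |
|---|---|---|---|
| 0 | 1.02 | 1.45 | 1.04 |
| 0.2 | 1.02 | 1.30 | 1.02 |
| 0.3 | 1.02 | 1.21 | 1.00 |
| 0.5 | 1.02 | 1.02 | 0.90 |
| 0.7 | 1.02 | 0.79 | 0.75 |

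Power at a true difference of 0.8 SD, in the same column order: 59% / 46% / 61% at ρ = 0.3; 59% / 59% / 70% at 0.5; 59% / 81% / 85% at 0.7.

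ANCOVA therefore loses very little at ρ = 0, gains essentially nothing at 0.2 and gains materially from about 0.5. Change is less precise than week-8 values whenever ρ is below 0.5.

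**2. Open variable.** In 200,000 simulated null trials per correlation (16/16), each test alone rejects in about 5%. At least one of week-8 and change rejects in 8.9% to 9.4% for ρ from 0.3 to 0.7, or about 9% per outcome.

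**3. Within-arm pattern, only if it were read as efficacy.** Suppose both arms have the same true change d, in SD of change. Then

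P(*N. sativa* significant in the direction of d, placebo not) = P(significant in that direction) × [1 − P(significant)],

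each factor from a one-sample noncentral t with n = 16 and noncentrality 4d.

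| d | 0 | 0.1 | 0.2 | 0.3 | 0.5 | 0.8 | 1.0 | 1.2 |
|---|---|---|---|---|---|---|---|---|
| Probability | 2.4% | 5% | 10% | 16% | 25% | 13% | 4% | 0.6% |

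The maximum is 25%, near d = 0.52, where each paired test has about 50% power: 0.5 × 0.5 = 0.25. A direct between-arm test rejects in that direction in about 2.5% of trials whatever the value of d.

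**The case against.** A reader might infer that the plan has no between-arm test, or that it will judge efficacy by significance in the *N. sativa* arm without significance in the placebo arm. The documents support neither. The independent test is named first, is held to the same threshold, and is most naturally the comparison with placebo. Nothing says that within-arm significance counts as efficacy. The 25% is therefore a conditional figure. It is also a maximum over the size of the shared change, and it falls below the 2.5% benchmark when that change is large. It shows why the paired tests should be labelled descriptive; it does not show that the plan is in error by that amount.

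It can also be said that an independent test on week-8 or change values is valid, that one sentence naming the variable and the deciding test would cure the ambiguity, and that the benefit of ANCOVA rests on a correlation the documents do not give. All of this stands. Baseline adjustment is the better choice, not the only valid one, and at low correlation it brings little. Against that, its worst case is a detectable difference of 1.04 instead of 1.02 SD, while at a correlation of 0.7 it is 0.75 instead of 1.02.

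Finally, much of the document is in the past tense. If the data have been analysed, the change cannot count as prespecified.

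**Conclusion.** The point holds in a limited form and should be fixed. The plan leaves the variable and the deciding role of its arm comparison unstated, ties only within-arm tests to before-and-after values under the same threshold, and does not use the collected baselines for adjustment. Baselines are explicit for blood samples and cytokines, and only inferred for SLEDAI.

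The cost of not adjusting runs from nothing at a pre-post correlation up to about 0.2, to a detectable difference of 1.02 instead of 0.90 SD at 0.5 and 1.02 instead of 0.75 SD at 0.7, relative to a week-8 t-test. The open choice between week-8 and change is worth about 9% instead of 5% false positives per outcome, if it were exploited. These sizes rest on 16 per arm, two-sided 0.05, normal data with equal SDs, and assumed correlations. The within-arm figure of up to 25% applies only under a decision rule that the plan does not state, so the conclusion does not rest on it.

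**What to change.** 1. For each outcome, state that the deciding analysis is the between-arm difference at week 8 adjusted for that outcome's baseline value (ANCOVA), with 95% CI.
2. Name one fallback for non-normal data, and its trigger, in advance. An example is ANCOVA on ranks of week-8 and baseline values if the model residuals fail a named normality check; the plan makes its tests conditional on normality but does not say how it is judged. A menu of fallbacks would reopen the choice after results. In 12,000 simulated null trials per correlation with log-normal data, taking the best of transformed ANCOVA, rank ANCOVA and Mann-Whitney on change gave 8.8% to 8.9% false positives. Mann-Whitney on change is also a poor default, since change scores lose precision at correlations below 0.5.
3. Report within-arm changes descriptively, and say that they are not evidence of efficacy.
4. Confirm that SLEDAI is scored at baseline and week 8.

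The minimum alternative is one sentence naming the variable of the independent test and saying that it decides.

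**Cost.** New wording and one model per outcome. The laboratory values are already collected, and SPSS, the plan's software, can fit the model. Claims of significant improvement within an arm are given up, and the roughly linear relation to baseline must be checked with only 32 patients. If the data have already been analysed, label this analysis post hoc.
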